1.3.3 Overall Benefit Risk

Taking into account the measures taken to minimize risk to subjects in this study, the potential risks identified in association with tapinarof are justified by the anticipated benefits that may be afforded to subjects with AD.

2 Objectives and Endpoints

The objectives and associated endpoints of the study are as follows:

Objectives	Associated Endpoint
Primary	
• To evaluate the efficacy of tapinarof cream, 1% QD compared with vehicle control in subjects with AD	• Proportion of subjects who have a validated Investigator Global Assessment in Atopic Dermatitis (vIGA-AD™) score of clear or almost clear (0 or 1) and at least a 2-grade reduction from Baseline at Week 8.
Secondary/Exploratory	
Secondary:
 
 • Proportion of subjects with $\geq 75\%$ improvement in EASI from Baseline at Week 8 • Mean change in %BSA affected from Baseline at Week 8 • Proportion of subjects with $\geq 90\%$ improvement in EASI from Baseline at Week 8 • Proportion of subjects ≥ 12 years old with a Baseline Peak Pruritus-Numeric Rating Scale (PP-NRS) score ≥ 4 who achieve ≥ 4-point reduction in the PP-NRS from Baseline at Week 8 
Exploratory:
 
• To evaluate the safety and tolerability of tapinarof cream, 1% QD in subjects with AD	
 • Incidence, frequency, and duration of TEAEs and serious adverse events (SAEs) • Change from Baseline in laboratory values • Change from Baseline in ECG parameters • Change from Baseline in vital signs • Mean Investigator-assessed local tolerability scale (LTS) scores by visit (overall and sensitive areas) • Mean subject (or caregiver)-assessed LTS scores by visit
• To describe the effect of tapinarof cream, 1% QD on AD symptom severity and the associated impact on daily activities and attitudes in subjects with AD	
 •  •  • 

Objectives	Associated Endpoint
	
● [REDACTED]● [REDACTED]
• To evaluate plasma concentrations of tapinarof in subjects with AD	
● Plasma concentration of tapinarof at Weeks 4 and 8

3 Study Design

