8.3.2 Follow-Up of Adverse Events

After the initial AE/SAE report, the Investigator is required to proactively follow each subject at subsequent visits/contacts. All SAEs and nonserious AEs will be followed until resolution, until the condition stabilizes, until the event is otherwise explained, or if the subject is lost to follow-up.

The Investigator will assess the outcome of each AE using the following criteria:

- **Recovered/Resolved:** The event has improved or subject recuperated.
- **Recovered/Resolved with sequelae:** The subject has recuperated but retained pathological conditions resulting from the prior disease or injury.
- **Recovering/Resolving:** The event is improving.
- **Not recovered/Not resolved:** The event has not improved or subject recuperated.
- **Unknown:** The outcome of the event is not known, not observed, not recorded, or refused.
- **Fatal:** Termination of life as an outcome of the AE.

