13. SAFETY ANALYSES

All safety analyses will be based on the safety population. No formal comparisons will be made for safety data.

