13.2 Adverse Events

All AE summaries will be restricted to TEAEs, which are defined as those AEs that occurred after dosing and those pre-existing AEs (prior to first application of study treatment) that worsened during the study. If it cannot be determined whether the AE is treatment emergent due to a partial onset date, then it will be counted as such. Verbatim terms in the eCRFs will be mapped to SOCs and PTs using MedDRA (Version 24.0). The one exception will be the summary of Any AE which will include AEs not considered treatment-emergent. The summary of Any AEs will be reported in the Overall Summary of Adverse Events.

For subjects not rolling over to the OL-LTE study, all reported AEs will be included in the Double-Blind phase summaries. For subjects rolling over to the OL-LTE study, all AEs with an onset date on or before the Week 8 visit date will be included in the Double-Blind phase summaries.

Imputation of start and end dates of AEs

To calculate duration of AEs, the following rules will be used where applicable to impute partial or completely missing start dates or end dates:

• If only the day is missing for a start date, the 1st of the month will be imputed. If the new estimated date falls before the date of first dose, while the known month and year match the month and year of the first dose, the date of first dose will be used as the new estimated date. The AE will be considered as a treatment-emergent AE (TEAE).

- If only the day is missing for an end date, the last day of the month will be imputed. If the new estimated date falls after the date of last study visit, the date of last study visit will be used as the new estimated date. Last study visit is defined as the Week 8 visit for those who elect to participate in the OL-LTE study, or the Week 9 follow-up visit for those who fail to qualify for participation in the OL-LTE study, or who qualify to participate but ultimately elect not to enroll.
- If both the day and the month are missing for a start date or end date, no imputation will be used, and the duration will not be calculated. However, if the year of start is the same or greater than the year of the first dose date, the AE will be considered as a TEAE.
- If the start date or end date is completely missing, duration will not be calculated. However, an event with completely missing start date will be considered as a TEAE.

Imputation of missing relationship and/or missing severity

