At each level of summarization, a subject will be counted once if he/she reported one or more events. The severity of TEAEs and relationship to study drug will be summarized in a similar manner. For summaries of relationship to study drug, a subject will be classified according related or not related. For summaries of TEAE CTCAE grade, a subject will be classified according to the worst grade.

For treatment-emergent AESIs, summarization will be more extensive, reflecting the more detailed information collected. Information summarized will include number of events per subject, earliest onset day, duration (in days), causality, grade, and seriousness of AESIs, outcome, actions taken with study drug, assorted physical characteristics of the AESIs, and demographic/baseline characteristics and vIGA-ADTM status. Each type of AESI will be summarized separately. If a subject has more than one treatment-emergent occurrence of an AESI, the subject's maximum duration, highest levels of causality and seriousness, maximum grade and generally the most extreme level of each characteristic will be summarized. If an AESI is ongoing at time of study completion/discontinuation, it will not be included in the duration summary.

A Kaplan-Meier figure will be generated for each treatment-emergent AESI of time to first event. Subjects not experiencing the AESI will be censored at the date of study completion or discontinuation.

For purposes of CT.gov reporting, two additional summaries of AEs by SOC, PT and treatment group will be done as follows:

- including only PTs >= 1% (in either treatment group)
- including only PTs \geq 5% (in either treatment group)

Each of these two summaries will include a total row summarizing the number of subjects with at least one of the PTs that meet the corresponding threshold.

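### SAP 13.2 leaves AESIs that are ongoing at study end out of the duration summary, so the durations shown tend to be too short whenever some are ongoing (descriptive safety table only)

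*SAP*

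**What the plan says.** SAP 13.2 plans an extended summary of each AESI type (contact dermatitis, follicular event, headache) that includes duration in days and outcome. Three rules in that section govern duration:

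- Ongoing events: "If an AESI is ongoing at time of study completion/discontinuation, it will not be included in the duration summary".
- Several occurrences: "If a subject has more than one treatment-emergent occurrence of an AESI, the subject's maximum duration" is the value summarized, in line with a general preference for the most extreme level of each characteristic.
- Missing dates: "If the start date or end date is completely missing, duration will not be calculated".

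The one time-to-event analysis of AESIs concerns onset, not resolution: "A Kaplan-Meier figure will be generated for each treatment-emergent AESI of time to first event".

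Follow-up in this study is short. In its rule for partial end dates, SAP 13.2 states: "Last study visit is defined as the Week 8 visit for those who elect to participate in the OL-LTE study". For subjects who complete without entering the extension, it is the Week 9 visit. Protocol 8.3.2 asks for longer follow-up of events: "All SAEs and nonserious AEs will be followed until resolution, until the condition stabilizes", among other end points.

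Protocol Section 2 lists as a safety endpoint "Incidence, frequency, and duration of TEAEs and serious adverse events (SAEs"). SAP 13 states: "No formal comparisons will be made for safety data".

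**The concern.** An AESI enters the duration summary only if it ends before the subject completes or discontinues. The chance of that falls as duration rises, so the summary describes a selected, shorter set of events. A reader could take the duration of resolved AESIs for the duration of AESIs in general.

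In the text of SAP 13.2, the AESI table is the only place where duration is summarized and not merely listed. It therefore carries the AESI part of a listed safety endpoint.

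The interaction with the maximum-duration rule is not specified. If ongoing episodes are removed before the maximum is taken, a subject with one short resolved episode and one long open episode is represented by the short one. That runs against the SAP's own preference for the most extreme value.

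**Working it through.** **The plan's own figure.** There is none to reproduce. The documents give no AESI durations, onset times or expected share ongoing.

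**Direction.** Let D be the duration and C the time from onset to the end of the subject's participation. The event is summarized only if D ≤ C. If D and C are independent, the summarized durations have density proportional to f(d) × P(C ≥ d). The weight P(C ≥ d) falls as d rises, so the summarized durations are stochastically shorter than all durations. If no event is ongoing, nothing is lost.

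**Illustrative size, one episode.** From the documents: cutoff at Day 57 (Week 8) or Day 64 (Week 9). Assumed: exponential durations with mean m, and onset uniform over T = 56 days from Day 1. With a = T/m and the Day 57 cutoff:

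- Share dropped = (1 − e^(−a))/a
- Mean of those kept = m × [g2 − g3/a] / (1 − share dropped), where g2 = 1 − (1 + a)e^(−a) and g3 = 2 − (a² + 2a + 2)e^(−a)

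For m = 14, a = 4:

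- Share dropped = (1 − 0.0183)/4 = 24.5%
- g2 = 0.9084 and g3 = 1.5238
- Mean kept = 14 × (0.9084 − 0.3809)/0.7546 = 9.8 days

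Simulation agrees with these formulas and supplies the Day 64 and early-onset columns:

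| True mean (days) | Dropped, Day 57 | Mean shown, Day 57 | Dropped, Day 64 | Mean shown, Day 64 | Mean shown, early onset (mean 14 days), Day 64 |
|---|---|---|---|---|---|
| 2 | 3.6% | 1.9 | 0.1% | 2.0 | 2.0 |
| 7 | 12.5% | 6.0 | 4.6% | 6.3 | 6.9 |
| 14 | 24.5% | 9.8 | 14.9% | 10.5 | 12.3 |
| 28 | 43.2% | 13.4 | 33.7% | 14.7 | 18.0 |
| 56 | 63.2% | 15.8 | 55.8% | 17.6 | 21.9 |

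**Does censoring recover the truth?** Medians for one episode, uniform onset, Day 57:

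| True mean | True median | Resolved only | Kaplan-Meier, ongoing censored |
|---|---|---|---|
| 7 | 4.9 | 4.2 | 4.9 |
| 14 | 9.7 | 7.2 | 9.7 |
| 28 | 19.4 | 10.4 | 19.4 |

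**Maximum-duration rule.** Two independent episodes per subject, same assumptions. The true median of the maximum is −m × ln(1 − √0.5).

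| True mean | True median of maximum | Ongoing dropped, then maximum | Longest so far, dropped if ongoing | First-episode Kaplan-Meier |
|---|---|---|---|---|
| 7 | 8.6 | 6.8 | 7.5 | 4.9 |
| 14 | 17.2 | 10.4 | 12.6 | 9.7 |
| 28 | 34.4 | 13.4 | 18.1 | 19.4 |

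Both readings of the current rule are too short, and the first is worse. First-episode Kaplan-Meier is correct for a single episode but estimates a different quantity. At means of 7 and 14 days it lies below either reading of the current rule.

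**Does later follow-up repair it?** Not as the rule is worded, because it turns on status at completion or discontinuation. An end date recorded afterwards does not bring the event back. Such dates could help a censored analysis. If end dates up to 28 days after Day 57 were recorded and used, the share without one would fall from 24.5% to 3.3% (mean 14) and from 43.2% to 15.9% (mean 28).

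**The case against.** The strongest reply is that this is an openly stated convention. A summary of resolved events is accurate for resolved events, and ongoing events can be found elsewhere: in the outcome summary within the same AESI table, the number of observations (SAP 6), the listings, and the narrative that Protocol 8.1 requires for every AESI. No test or decision hangs on the row, and the size could be negligible. The table shells are not in the public text and may already carry a label.

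Much of this stands. It is why the point concerns a descriptive table and claims no particular size. But those sources only show that events were ongoing; none corrects the duration figure, and a footnote would disclose the exclusion without removing its effect.

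A second reply is that Kaplan-Meier on first episodes should not displace the per-subject maximum, because it ignores later, longer episodes and can report shorter durations. That stands in full and shapes the fix.

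Two stronger readings are tempting, and the documents support neither.

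- **A biased comparison between arms.** The documents give no durations by arm and plan no formal safety comparison. The sample-size section assumes 15% loss on tapinarof and 30% on vehicle. In a simulation with equal true durations in both arms, uniform withdrawal times and a 57-day window, that difference alone moves the mean shown only from 9.7 to 9.6 days (true mean 14) or from 13.3 to 13.1 (true mean 28).
- **A failure of the whole duration endpoint.** The endpoint covers all TEAEs and SAEs; the exclusion touches only the AESI summary.

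**Conclusion.** The point holds for the AESI duration table. Excluding ongoing events makes the summarized durations tend to be too short whenever some AESIs are ongoing. The direction rests on duration being roughly independent of time from onset to study end.

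The size is unknown. Under the assumed exponential durations it runs from almost nothing for events of a few days to about half at a true mean of 28 days (13.4 against 28, Day 57, uniform onset). It shrinks with earlier onset and vanishes if nothing is ongoing. No efficacy result, test or sample-size figure is affected. The change is worth making because the bias is predictable and the remedy is cheap.

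**What to change.** In SAP 13.2:

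1. Keep the per-subject maximum duration and label the row 'resolved events only'.
2. State the order of the two rules: a subject whose longest episode so far is ongoing is left out of that row, and is not represented by a shorter resolved episode.
3. Show the number and percent of subjects with an ongoing AESI, by AESI type and treatment.
4. Add beside it a Kaplan-Meier summary of time to resolution (median and quartiles where estimable) of each subject's first treatment-emergent episode, by AESI type and treatment. Censor unresolved episodes at the last date their status was recorded in this study.
5. Leave out of that summary, and count, episodes with an unknown start date or resolved with an unknown end date. Say how the Fatal and Unknown outcomes of Protocol 8.3.2 are treated, and how later recorded end dates fit with the rule that caps imputed partial end dates at the last study visit.

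The cost is a few sentences and one descriptive table, using the dates and outcomes already listed for each AE. If the blind has been broken, SAP 6 would make the added analysis post hoc.

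Downsides:

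- **Few events.** Under the Day 57 assumptions with a true mean of 28 days, the median is inestimable in 8.1% of samples of 10 events and 1.9% of samples of 20; the upper quartile in 39.2% and 31.2%. With a true mean of 14 days the median figures are 0.4% and 0.0%, and the upper-quartile figures 7.8% and 2.2%.
- **Informative censoring.** Protocol 4.6.1 withdraws subjects for related Grade 3 or 4 events, so censoring may depend on the event. In one assumed case, 20% of subjects had events twice as long and stopped 1 to 14 days after onset if still affected, with a mean of 28 days for the other events. The true median was 22.0, Kaplan-Meier censored at the last visit gave 20.3, and resolved-only gave 9.8.
- **A different quantity.** The first-episode estimate is often shorter than the per-subject maximum, so it must not replace it. Nor should Kaplan-Meier be run on the maximum with censoring whenever any episode is ongoing. In the two-episode case that gave medians of 9.0, 19.0 and 42.6 against true values of 8.6, 17.2 and 34.4.

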4.7 Lost to Follow-Up

A subject is considered lost to follow-up if he/she repeatedly fails to return to the study site for scheduled visits and is unable to be contacted by the study site. The following actions must be taken if a subject fails to return to the clinic for a required study visit:

- The site must attempt to contact the subject or caregiver and reschedule the missed visit as soon as possible, counsel the subject on the importance of maintaining the assigned visit schedule, and ascertain whether or not the subject wishes to and/or should continue in the study.
- Before a subject is deemed lost to follow-up, the Investigator or designee must make every effort to regain contact with the subject or caregiver (where possible, 3 telephone calls and, if necessary, a certified letter to the subject's last known mailing address or local equivalent methods). These contact attempts should be documented in the subject's medical record.
- Should the subject or caregiver continue to be unreachable, he/she will be considered to have withdrawn from the study with a primary reason of lost to follow-up. In this case, the discontinuation date will be listed as the date the certified letter was mailed to the subject.

5 Study Treatment

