10.2 Determination of Sample Size

It is estimated that the proportion of subjects who will achieve a vIGA-AD™ score of 0 or 1 and at least a 2-grade reduction from Baseline at Week 8 will be 45% for subjects receiving tapinarof compared with 25% for subjects receiving vehicle control, based upon the Phase 2 results. With 400 subjects randomized in a 2:1 ratio (267 subjects receiving tapinarof, and 133 subjects receiving vehicle control), this will provide 97.2% power for statistical significance (2-sided $p < 0.05$). The power is calculated from a Fisher Exact sample size calculation. It is assumed that 15% of the subjects receiving tapinarof will be lost to follow-up by 8 weeks compared with 30% of the subjects receiving vehicle control. These subjects will be included in the primary analysis using the multiple imputation method.

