5. DETERMINATION OF SAMPLE SIZE

It is estimated that the proportion of subjects who will achieve a vIGA-ADTM score of 0 or 1 and at least a 2-grade reduction from Baseline to Week 8 will be 45% for subjects receiving tapinarof compared with 25% for subjects receiving vehicle control, based upon the Phase 2 results. With 400 subjects randomized in a 2:1 ratio (267 subjects receiving tapinarof, and 133 subjects receiving vehicle control), this will provide 97.2% power for statistical significance (2-sided p <0.05). The power is calculated from a Fisher Exact sample size calculation. It is assumed that 15% of the subjects receiving tapinarof will be lost to follow-up by 8 weeks compared with 30% of the subjects receiving vehicle control. These subjects will be included in the primary analysis using the multiple imputation method.

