9. STUDY POPULATION

9.1 Subject Disposition

Subject disposition information will be summarized for all subjects by treatment and overall. Summaries will include: the number of subjects screened, the number of enrolled (randomized) subjects, the number of subjects in each population, the number of subjects completing the treatment phase of the study, the number of subjects completing the study through follow-up and primary reason for discontinuation, and number of days in the study (defined as study completion/discontinuation date – treatment start date + 1).

In order to describe the impact of COVID-19 on current study, the following disposition events will be summarized in the tables separately:

- Subjects discontinued from the treatment/study as a result of a positive COVID-19 diagnosis.
- Subjects discontinued from the treatment/study due to other reasons related to COVID-19. This is excluding COVID-19 diagnosis but may include reasons such as site closure, travel restrictions, fear of infection, etc.
- Subjects with study visits altered (including modified in-clinic visit, virtual and phone visits) and missed due to COVID-19.

COVID-19 related protocol deviations will be summarized separately. The impact of COVID-19 (including protocol deviation, visit alteration, treatment/study discontinuation and diagnosis of COVID-19) will also be flagged at subject-level in a data listing. Subject profile will be used to compile all COVID-19 related information for affected subjects.

Also, all COVID-19 related symptoms and confirmed cases that occur during the study will be reported as AEs and included in the summaries.

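### The AESI Kaplan-Meier figures censor lost subjects at the date the certified letter was mailed, so time after last contact counts as event-free and the curves run slightly low in both arms

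*SAP*

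**What the plan says.** SAP 13.2 plans one Kaplan-Meier figure of time to first event for each AESI: contact dermatitis, follicular event and headache. Its censoring rule is one sentence: "Subjects not experiencing the AESI will be censored at the date of study completion or discontinuation". It makes no exception for subjects lost to follow-up.

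Protocol 4.7 defines a lost subject as one who "repeatedly fails to return to the study site for scheduled visits and is unable to be contacted by the study site". Before that status is assigned, the site tries to reschedule and to regain contact: "where possible, 3 telephone calls and, if necessary, a certified letter to the subject's last known mailing address". If this fails, "the discontinuation date will be listed as the date the certified letter was mailed to the subject". No time limit is set for these steps.

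Protocol 6.3.1 collects adverse events only up to the final visit or contact with the subject. The sample-size sections (Protocol 10.2, SAP 5) assume that "15% of the subjects receiving tapinarof will be lost to follow-up by 8 weeks compared with 30% of the subjects receiving vehicle control".

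**The concern.** A censoring time should be the last time at which the subject is known to be event-free. For a lost subject, that is the last visit or call at which AEs were asked about. Read together, Protocol 4.7 and SAP 13.2 use a later date. Between the two dates the subject sits in the denominator, but no event of theirs can enter the numerator. The estimated hazard is diluted and the cumulative incidence curve is too low.

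If the arms lose subjects at different rates, the dilution differs too, so two arms with the same true incidence would be plotted apart. These are the events that Protocol 8.1.3 singles out as clinically important, and the figures give the time course that crude percentages do not.

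**Working it through.** **Inputs from the documents.** Arms: "267 subjects receiving tapinarof, and 133 subjects receiving vehicle control". Planned loss by Week 8: 15% and 30%. AE contacts: clinic at Weeks 1, 2, 4 and 8, phone at Weeks 3 and 6.

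**Inputs not in the documents (assumed).** The gap from last contact to letter, the share of planned loss that is letter-dated, the AESI incidence and the shape of its hazard.

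**The plan's own figure.** The documents give no number for the censoring rule. The stated power of 97.2% ("45% for subjects receiving tapinarof compared with 25% for subjects receiving vehicle control", Fisher exact, two-sided 0.05) is reproduced closely: 97.6% by exact calculation and 97.3% by the continuity-corrected normal approximation. It does not use the censoring date.

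**Step 1: unobserved time.** Planned loss is 0.15 × 267 ≈ 40 on tapinarof and 0.30 × 133 ≈ 40 on vehicle. If all are letter-dated, each week of gap adds about 40 unobserved person-weeks per arm. Per randomised subject that is 40/267 = 0.15 week against 40/133 = 0.30 week.

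**Step 2: effect on the curve.** The plotted hazard equals the true hazard times (share still in contact) / (share counted at risk). Take all planned loss as letter-dated, last contact spread evenly over Weeks 1, 2, 3, 4 and 6, and a 4-week gap. Each contact time then carries 0.30/5 = 0.06 of vehicle subjects and 0.15/5 = 0.03 of tapinarof subjects. Ignoring the small depletion by events:

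| Weeks | Vehicle | Ratio | Tapinarof | Ratio |
|---|---|---|---|---|
| 0-1 | 1.00/1.00 | 1.000 | 1.00/1.00 | 1.000 |
| 1-2 | 0.94/1.00 | 0.940 | 0.97/1.00 | 0.970 |
| 2-3 | 0.88/1.00 | 0.880 | 0.94/1.00 | 0.940 |
| 3-4 | 0.82/1.00 | 0.820 | 0.91/1.00 | 0.910 |
| 4-5 | 0.76/1.00 | 0.760 | 0.88/1.00 | 0.880 |
| 5-6 | 0.76/0.94 | 0.809 | 0.88/0.97 | 0.907 |
| 6-7 | 0.70/0.88 | 0.795 | 0.85/0.94 | 0.904 |
| 7-8 | 0.70/0.82 | 0.854 | 0.85/0.91 | 0.934 |
| Mean | | 0.857 | | 0.931 |

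With a true 8-week incidence of 10% and constant hazard, the cumulative hazard is −ln(0.90) = 0.1054. Plotted incidence:

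- vehicle: 1 − exp(−0.857 × 0.1054) = 8.6%
- tapinarof: 1 − exp(−0.931 × 0.1054) = 9.3%

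A simulation of the same setting gives 8.6% and 9.3%. Censoring at last contact returns 10.0% in both arms.

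**Step 3: range, by the same formula with a true 10% in both arms.**

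| Share letter-dated | Gap | Tapinarof | Vehicle |
|---|---|---|---|
| one third (5%/10%) | 1 week | 9.9% | 9.9% |
| one third | 21-42 days | 9.8% | 9.5% |
| all (15%/30%) | 1 week | 9.8% | 9.6% |
| all | 2 weeks | 9.6% | 9.2% |
| all | 4 weeks | 9.3% | 8.6% |
| all | 28-56 days | 9.1% | 8.2% |

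In the first row the mean ratios are 0.994 and 0.987, so 1 − exp(−0.994 × 0.1054) and 1 − exp(−0.987 × 0.1054) both round to 9.9%. The rows with a day range spread the gap evenly over it and add Day 1 as a possible last contact. Simulated values agree to within about 0.1 point (8.1% for vehicle in the last row).

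If the hazard is instead front-loaded (exponential decay with a 14-day constant, an assumption), the last row becomes about 9.4% and 8.9%. At other true incidences, with all loss letter-dated and a 4-week gap, simulation gives 4.7% and 4.3% for a true 5%, and 18.7% and 17.3% for a true 20%.

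**The case against.** The strongest reply is that the effect is small and its size uncertain. Most of that stands.

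- **Loss rates.** The 15% and 30% are planning figures, and the documents do not split them by reason. Subjects who withdraw and attend the Early Termination visit have AEs recorded there, so their gap is about zero. The letter rule reaches only those who stay unreachable, so treating all planned loss as letter-dated gives an upper scenario.
- **Delay.** Protocol 4.7 asks for prompt contact after a missed visit, so short gaps are possible. Against that, the definition requires repeated missed visits, and clinic visits after Week 2 are 2 and 4 weeks apart.
- **Consequence.** Safety comparisons are descriptive, and the crude AESI summaries do not use the censoring date.

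Three stronger readings are tempting, and the documents do not support them.

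- **AESI incidence as a whole is understated.** Only the three Kaplan-Meier figures are.
- **The rule flatters tapinarof against vehicle.** With higher vehicle loss, the vehicle curve is lowered more in relative terms, so the incidence ratio moves against tapinarof. With equal true incidence the difference does too. The absolute difference could narrow only if tapinarof's incidence were well above vehicle's: with a 4-week gap, a true 20% against 5% would plot as 18.7% against 4.3%, or 14.4 points instead of 15. Tapinarof's own curve is low in every case.
- **SAP 9.1 is wrong as well**, because it reports "number of days in the study (defined as study completion/discontinuation date" less treatment start plus one. That is a disposition measure defined to the recorded date. Exposure is computed separately in SAP 13.1, from first to last dose, so nothing there is inflated.

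**Conclusion.** The rule is wrong as written, and the point is minor. No SAP provision overrides the combination of Protocol 4.7 and SAP 13.2, so each letter-dated subject without the AESI contributes unobserved time as event-free time. The direction, downward in both arms, does not depend on any assumption.

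That vehicle is affected more does depend on one: that vehicle loss is in fact higher, as planned. The size depends on the delay, the letter-dated share and the hazard. At a true 10%, the shortfall runs from about 0.1 point in each arm to about 0.9 point on tapinarof and 1.8 to 1.9 points on vehicle, the upper end requiring every assumption to be unfavourable. Crude AE incidence tables, efficacy tests and the power statement are not touched.

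**What to change.** In SAP 13.2, replace the censoring sentence with a rule of this kind: subjects without the AESI are censored at the last clinic visit (including early termination and unscheduled visits) or phone contact at which adverse events were assessed, no later than the date of study completion or discontinuation. State the rule in a footnote to the three figures.

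Keep the letter date as the administrative disposition date, and leave the SAP 9.1 definition of days in study unchanged.

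The cost is one SAP sentence and one derived date per subject. AE assessment is already scheduled at every visit and phone contact, so no new data are needed. No clinical procedure or efficacy analysis changes.
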